5.2.6.1.2 Serious adverse event

A serious adverse event (SAE) is defined as any AE, which fulfils at least one of the following criteria:

- results in death,
- is life-threatening, which refers to an event in which the patient was at risk of death at the time of the event; it does not refer to an event that hypothetically might have caused death if more severe,
- requires inpatient hospitalisation or prolongation of existing hospitalisation
- results in persistent or significant disability or incapacity,
- is a congenital anomaly / birth defect,
- is deemed serious for any other reason if it is an important medical event when based on appropriate medical judgement which may jeopardise the patient and may require medical or surgical intervention to prevent one of the other outcomes listed in the above definitions. Examples of such events are intensive treatment in an emergency room or at home for allergic bronchospasm, blood dyscrasias or convulsions that do not result in hospitalisation or development of dependency or abuse.

5.2.6.1.3 AEs considered “Always Serious”

In accordance with the European Medicines Agency initiative on Important Medical Events, Boehringer Ingelheim has set up a list of AEs, which by their nature, can always be considered to be “serious” even though they may not have met the criteria of an SAE as defined above.

The latest list of “Always Serious AEs” can be found in the electronic data capture system. A copy of the latest list of “Always Serious AEs” will be provided upon request. These events should always be reported as SAEs as described in [Section 5.2.6.2](#).

Cancers of new histology and exacerbations of existing cancer must be classified as a serious event regardless of the time since discontinuation of the drug and must be reported as described in [5.2.6.2](#), subsections “AE Collection” and “**AE reporting to sponsor and timelines**”.

5.2.6.1.4 Adverse events of special interest

The term adverse events of special interest (AESI) relates to any specific AE that has been identified at the project level as being of particular concern for prospective safety monitoring and safety assessment within this trial, e.g. the potential for AEs based on knowledge from other compounds in the same class. AESIs need to be reported to the sponsor’s Pharmacovigilance Department within the same timeframe that applies to SAEs, please see Section [5.2.6.2.2](#).

The following are considered as AESIs:

Hepatic injury

A hepatic injury is defined by the following alterations of hepatic laboratory parameters:

Proprietary confidential information © 2021 Boehringer Ingelheim International GmbH or one or more of its affiliated companies

- an elevation of AST (Aspartate Aminotransferase) and/or ALT (Alanine Aminotransferase) ≥ 3 fold ULN combined with an elevation of total bilirubin ≥ 2 fold ULN measured in the same blood draw sample, or
- aminotransferase (ALT, and/or AST) elevations ≥ 10 fold ULN.

These lab findings constitute a hepatic injury alert and the patients showing these lab abnormalities need to be followed up according to the “DILI checklist” provided in the ISF. In case of clinical symptoms of hepatic injury (icterus, unexplained encephalopathy, unexplained coagulopathy, right upper quadrant abdominal pain, etc.) without lab results (ALT, AST, total bilirubin) available, the investigator should make sure these parameters are analysed, if necessary in an unscheduled blood test. Should the results meet the criteria of hepatic injury alert, the procedures described in the DILI checklist should be followed.

5.2.6.1.5 Intensity (severity) of AEs

The intensity (severity) of the AE should be judged based on the following:

Mild: Awareness of sign(s) or symptom(s) that is/are easily tolerated.
Moderate: Sufficient discomfort to cause interference with usual activity.
Severe: Incapacitating or causing inability to work or to perform usual activities.

5.2.6.1.6 Causal relationship of AEs

Medical judgement should be used to determine whether there is a reasonable possibility of a causal relationship between the adverse event and the given study treatment, considering all relevant factors, including pattern of reaction, temporal relationship, de-challenge or re-challenge, confounding factors such as concomitant medication, concomitant diseases and relevant history.

Arguments that may suggest that there is a reasonable possibility of a causal relationship could be:

- The event is consistent with the known pharmacology of the drug.
- The event is known to be caused by or attributed to the drug class.
- A plausible time to onset of the event relative to the time of drug exposure.
- Evidence that the event is reproducible when the drug is re-introduced.
- No medically sound alternative aetiologies that could explain the event (e.g. pre-existing or concomitant diseases, or co-medications).
- The event is typically drug-related and infrequent in the general population not exposed to drugs (e.g. Stevens-Johnson syndrome).
- An indication of dose-response (i.e. greater effect size if the dose is increased, smaller effect size if dose is reduced).

Arguments that may suggest that there is no reasonable possibility of a causal relationship could be:

- No plausible time to onset of the event relative to the time of drug exposure is evident (e.g. pre-treatment cases, diagnosis of cancer or chronic disease within days / weeks

Proprietary confidential information © 2021 Boehringer Ingelheim International GmbH or one or more of its affiliated companies

of drug administration; an allergic reaction weeks after discontinuation of the drug concerned).

- Continuation of the event despite the withdrawal of the medication, taking into account the pharmacological properties of the compound (e.g. after 5 half-lives). Of note, this criterion may not be applicable to events whose time course is prolonged despite removing the original trigger.
- Additional arguments amongst those stated before, like alternative explanation (e.g. situations where other drugs or underlying diseases appear to provide a more likely explanation for the observed event than the drug concerned).
- Disappearance of the event even though the trial drug treatment continues or remains unchanged.

5.2.6.2 Adverse event collection and reporting

5.2.6.2.1 AE Collection

The investigator shall maintain and keep detailed records of all AEs in the patient files. The following must be collected and documented on the appropriate CRF(s) by the investigator:

- From signing the informed consent onwards until the follow-up Visit 1: all AEs (non-serious and serious) and all AESIs.
- After follow-up Visit 1 until the individual patient's end of trial: cancers of new histology and exacerbations of existing cancers, all trial treatment related SAEs and all trial treatment related AESIs.
- After the individual patient's end of trial:
the investigator does not need to actively monitor the patient for new AEs but should only report any occurrence of cancer and trial treatment related SAEs and trial treatment related AESIs of which the investigator may become aware of by any means of communication, e.g. phone call. Those AEs should be reported on the BI SAE form (see [Section 5.2.6.2.2](#)), but not on the CRF.

Vital Status Data Collection

Patients who discontinue trial medication prematurely, who agree to be contacted further, but do not agree to physical visits, should be followed up as described in [Section 3.3.4.1](#), withdrawal from trial treatment. From then on until the individual patient's end of the trial the investigator must report all deaths/fatal AEs regardless of relationship, and trial treatment related SAEs and trial treatment related AESIs the investigator becomes aware of.

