| Comparator product(s) | Placebo to BI 764198 |
| dose | Not applicable |
| mode of administration | Oral (p.o.) or, only if needed, nasogastric intubation |
| Duration of treatment | Up to 28 days |
| Statistical methods | 
The primary endpoint will be analysed with a logistic regression model using covariates of treatment, severity grade at baseline, age, creatinine at baseline, and duration of symptoms before hospitalisation, to evaluate the absolute difference in proportions of patients alive and free of mechanical ventilation at Day 29 with BI 764198 and placebo. Patients who terminate the study medication prematurely will be followed and the events which occur after premature discontinuation of medication and before the time point of interest will be included in the analysis using the Full Analysis Set (FAS).
 
The logistic regression for the primary endpoint analysis will be used for other binary endpoint(s) and time-to-event endpoints will be analysed using Cox regression including covariates used for the primary analysis. Ventilator free days will be analysed using ANCOVA including the same covariates as in the primary analysis.
 |

FLOW CHART

| Trial Periods | Screening | Treatment | | | Follow-up (telephone visits only ^b) | | |
|--|----------------------|---------------|---------------------------|---|--|-----------------------|-----------------------------|
| | | 1 | 2 | 3 through 29 | EOT ^a | FUP ^b 1 | FUP ^b 2, 3, 4 |
| Visit | | | | | | | |
| Day | -1 | 1 | | Daily Day 2 through discharge -1 day (maximum Day 28) | discharge/ day after last dose | EOT +4 days | 15, 29, 60 (from Day 1) |
| Time window for visits (days) | -3 to 1 ^c | | | | | +2 | ±3 |
| Informed Consent | X | | | | | | |
| Demographics | X | | | | | | |
| Medical History | X | | | | | | |
| Baseline Conditions | X | | | | | | |
| Clinical Frailty Scale (CFS) | X | | | | | | |
| SARS-CoV-2 PCR test ^{c,h} | X | | | | | | |
| Review of inclusion/exclusion criteria ^c | X | X | | | | | |
| Randomisation | | X | | | | | |
| Concomitant Therapy and Procedures | X | X | X | X | X | X | X |
| Adverse event evaluation | X | X | X | X | X | X | X |
| Hospitalisation Status | X | X | X | X | X | X | X |
| World Health Organization (WHO) Clinical Progression Scale | X | X | X | X | X ^f | X ^f | |
| Ventilation and oxygen parameters; respiratory rate, FiO ₂ , SpO ₂ | X | X | X | X | X ^f | X ^f | |
| Vital signs (refer to Section 5.2.2) | X | X | X | X | | | |

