3.3.4.1 Discontinuation of trial treatment

An individual patient will discontinue trial treatment if:

- The patient wants to discontinue trial treatment, without the need to justify the decision.
- The patient has repeatedly shown to be non-compliant with important trial procedures and, in the opinion of both, the investigator and sponsor representative, is not willing or able to adhere to the trial requirements in the future.
- The patient needs to take concomitant medication that interferes with the investigational medicinal product or other trial treatment.
- The patient can no longer receive trial treatment for medical reasons (such as surgery, adverse events, other diseases, or pregnancy).

Proprietary confidential information © 2021 Boehringer Ingelheim International GmbH or one or more of its affiliated companies

- The patient experiences renal impairment based on clinical judgement (e.g. sustained eGFR <30 mL/min/1.73 m²).
- The patient experiences hepatic impairment based on clinical judgement (e.g. ALT/AST >5 × ULN).
- The patient experiences QT prolongation of the QTc interval of either >60 ms change from baseline or greater than 500 ms during the study.

Should a patient become pregnant during the trial, study medication will be stopped and the patient will be followed up until birth or otherwise termination of the pregnancy. The data of the patient will be collected until Last Patient Completed and reported in the clinical trial report. Any events thereafter will be reported in the BI Pharmacovigilance database. For further details on pregnancy reporting, refer to [Section 5.2.6.2.3](#).

If new efficacy/safety information becomes available, Boehringer Ingelheim will review the benefit-risk-assessment and, if needed, pause or discontinue the trial treatment for all patients or take any other appropriate action to guarantee the safety of the trial patients.

Even if the trial treatment is discontinued, the patients remain in the trial and, given their agreement, will undergo the procedures for early treatment discontinuation, follow-up, and vital status collection as outlined in the [Flow Chart](#) and [Section 6.2.3](#).

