6.2.3 Follow-up period and trial completion

For all randomised patients, termination of trial medication and trial completion must be recorded on the corresponding eCRFs.

Applicable FUP visits and EOS visits will be conducted remotely by a phone contact for all patients that have completed treatment, EOT visit, and discharge. Each of these visits includes vital status.

FUP visits should be conducted as follows:

- FUP 1 should be performed 4 days after EOT visit for all patients.
- FUP 2 and FUP 3 which correspond to study Day 15 and Day 29 after start of therapy, should be performed *if the time point is applicable after drug discontinuation*. FUP 2 and FUP 3 visits should not be conducted within +/- 2 days of EOT or FUP 1.
- FUP 4 and EOS which correspond to study Day 60 and Day 90 will be performed for all patients.

If a patient remains hospitalized after EOT visit, applicable FUP visits and the EOS visit will be conducted in hospital until discharge and thereafter by telephone.

If a patient withdraws participation from the study, it may be agreed to collect vital status per the remaining originally planned visit schedule according to the [Flow Chart](#).

Trial completion is defined as patients completing the FUP and EOS visits according to the [Flow Chart](#).

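### Protocol 5.2.6.2.1 gives two unreconciled AE-collection rules, up to FUP 1, for patients who stop drug early and decline physical visits

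*Protocol*

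**What the plan says.** Protocol 5.2.6.2.1 sets the general rule in its first bullet: "From signing the informed consent onwards until the follow-up Visit 1: all AEs (non-serious and serious) and all AESIs". The bullet makes no exception for patients who stop drug early.

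The same section ends with a paragraph on vital status. It concerns "Patients who discontinue trial medication prematurely, who agree to be contacted further, but do not agree to physical visits". It sends them to Protocol 3.3.4.1 for follow-up and then sets a shorter list, which runs from that point, and not from FUP 1, to the patient's end of trial: "the investigator must report all deaths/fatal AEs regardless of relationship, and trial treatment related SAEs". Treatment-related AESIs are added, and the related events are limited to those the investigator becomes aware of.

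Three other places bear on the same patients:

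- Protocol 3.3.4.1 says that patients who stop treatment stay in the trial and, if they agree, "will undergo the procedures for early treatment discontinuation, follow-up, and vital status collection as outlined in the" Flow Chart and 6.2.3.
- The Flow Chart heads the later period "Follow-up (telephone visits only", with a footnote allowing in-hospital contacts for patients not yet discharged. Its AE row is marked throughout: "Adverse event evaluation | X | X | X | X | X | X | X". Protocol 6.2.3 schedules FUP 1 for all patients.
- Protocol 5.2.6.2.2 requires SAEs and AESIs to be sent to the sponsor within 24 hours, with no limit to related events and no carve-out for this subset.

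**The concern.** Between the early stop and FUP 1, one patient falls under two rules that ask for different things. The text does not say which prevails. The narrower rule is also passive, because part of it covers only what reaches the investigator.

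The trigger does not explain the narrowing. These patients refuse physical visits but accept contact, and after discharge FUP 1 is a telephone call. Other discharged patients give a full AE account by telephone at the same point.

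What is at stake is safety ascertainment in a group that need not be a random sample. The reasons for stopping in Protocol 3.3.4.1 include adverse events, renal or hepatic impairment and QT prolongation. SAP section 7 takes percentages over all patients in the set whether or not data are missing, and SAP 7.8.1 counts patients with events. An event that is never collected therefore enters the tables as no event.

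**Working it through.** The plan states no figure to reproduce. The check is a comparison of the rules, plus the length of the overlap.

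**Which events each rule requires before FUP 1, for this subset**

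| Event | 5.2.6.2.1, first bullet | 5.2.6.2.1, vital-status paragraph | 5.2.6.2.2, 24-hour report |
|---|---|---|---|
| Fatal AE | yes | yes | yes (serious by definition) |
| Related SAE or AESI | yes | yes, if the investigator becomes aware | yes |
| Unrelated non-fatal SAE or AESI | yes | not listed | yes |
| Non-serious AE that is not an AESI | yes | not listed | only if relevant to a reported SAE or AESI |

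The last row is the clearest gap: if the vital-status paragraph is taken to replace the first bullet, no other rule generally picks these events up. The third row is less exposed, because 5.2.6.2.2 still asks for those events. A site could nevertheless treat the subset paragraph as the specific rule that overrides it.

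**Length of the overlap**

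- EOT = last dose + 1 day (Protocol 6.2.2).
- FUP 1 = EOT + 4 days (Protocol 6.2.3), window +2 (Flow Chart).
- FUP 1 therefore falls at last dose + 1 + 4 = 5 days, up to last dose + 1 + 4 + 2 = 7 days.

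The overlap is at most these 5 to 7 days when visits run to schedule. It is shorter if the patient declines physical visits some days after the last dose.

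**How much reaches the analysis**

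Protocol 7.2.5 counts AEs as treatment-emergent from the start of treatment to the end of the residual effect period (REP). SAP 7.8.1 puts later AEs in listings only. If the REP lasts R days after the last dose, the affected days that count are the smaller of R and the 5 to 7 days. R is not visible in the documents.

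The number of patients affected in an arm would be the number in the subset times the share of them with an uncollected event that matters for the table in question. The documents give neither factor. Two limits still follow:

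- The loss in any patient-count table cannot exceed the number of subset patients in that arm.
- A patient who already had an AE on treatment is already in the any-AE count. That table is less exposed than the counts by system organ class and preferred term.

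**The case against.** The strongest reply is that the vital-status paragraph sets a floor and not a limit. The bullets govern what must be collected on the CRF, whereas the paragraph states what must be reported and stands under a vital-status heading. It first refers to 3.3.4.1, and so to a Flow Chart that still schedules AE evaluation at EOT and FUP 1. On that reading nothing is lost.

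This reading is possible, and it is why under-counting cannot be asserted as fact. It does not settle the matter. As a floor the sentence would add nothing before FUP 1, where the first bullet already requires everything, yet its start is not tied to FUP 1. A site can reasonably take it as permission to collect less.

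Second, the subset is probably small. Patients are in hospital during treatment, may stop drug when fit for discharge, and are then followed by telephone, so few have physical visits left to refuse. This stands.

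Third, the telephone sentence in 6.2.3, "FUP visits and EOS visits will be conducted remotely by a phone contact for all patients", goes on to limit itself to those who have completed treatment, the EOT visit and discharge. A patient who refuses the EOT visit is not strictly within it. That is a fair point on wording, but FUP 1 is still required for all patients, and this group has agreed to contact.

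A reader might also infer that fatal AEs are poorly covered after FUP 1, because unrelated ones are named only for this subset. The documents do not support a loss there. Vital status is collected at each follow-up contact, and SAP 7.5.2 compares mortality between arms at Days 15, 29, 60 and 90.

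**Conclusion.** The two rules in Protocol 5.2.6.2.1 conflict for patients who stop drug early, accept contact and decline physical visits, and the narrower one has no evident need before FUP 1. If sites follow it, non-serious AEs, and possibly unrelated non-fatal SAEs and AESIs despite 5.2.6.2.2, may go uncollected for up to 5 to 7 days after the last dose.

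This is a minor point. The time span rests on EOT and FUP 1 taking place on schedule. No percentage should be attached to the loss: the subset size, the AE rate and any difference between arms are not in the documents, and the REP is blacked out.

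Two stronger readings go too far. One is that AEs after any early stop are under-counted. Early stoppers who accept visits stay under the all-AE rule, and even for the subset the loss depends on how sites read the text. The other is that harm would be hidden in one arm. That needs an imbalance in the subset that nothing in the documents shows.

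**What to change.** Reword the vital-status paragraph of Protocol 5.2.6.2.1 to say, in substance: patients who stop trial medication early and agree to contact, with or without physical visits, remain under collection of all AEs and AESIs until FUP 1, obtained by telephone or from the hospital record. The shorter list (deaths and fatal AEs regardless of relationship, related SAEs, related AESIs) applies only after FUP 1, until the patient's end of trial. A cross-reference to 5.2.6.2.2 would confirm that the 24-hour duty is unchanged.

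The cost is one reworded paragraph and a short note to sites. The FUP 1 contact is already planned, so no visit is added; sites complete a few more AE entries for a small group. The collection rules for other patients after FUP 1 need no change on this account.

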5.2.6.2.2 AE reporting to the sponsor and timelines

The investigator must report SAEs (including "Always serious" events, even though they may not have met the criteria of an SAE), AESIs, and non-serious AEs which are relevant for the reported SAE or AESI, on the BI SAE form immediately (within 24 hours) to the sponsor's unique entry point (country specific reporting process will be provided in the ISF). The same timeline applies if follow-up information becomes available. In specific occasions, the investigator could inform the sponsor upfront via telephone. This does not replace the requirement to complete and send the BI SAE form.

With receipt of any further information to these events, a follow-up SAE form has to be provided. For follow-up information the same rules and timeline apply as for initial information. All (S)AEs, including those persisting after individual patient's end of trial must be followed up until they have resolved, have been assessed as "chronic" or "stable", or no further information can be obtained.

5.2.6.2.3 Pregnancy

In rare cases, pregnancy might occur in a clinical trial. Once a patient has been enrolled in the clinical trial and has taken trial medication, the investigator must report any drug exposure during pregnancy in a trial participant immediately (within 24 hours) by means of Part A of the Pregnancy Monitoring Form to the sponsor's unique entry point.

Similarly, potential drug exposure during pregnancy must be reported if a partner of a male trial participant becomes pregnant. This requires written consent of the pregnant partner. Reporting and consenting must be in line with local regulations. The ISF will contain the trial specific information and consent for the pregnant partner.

The outcome of the pregnancy associated with the drug exposure during pregnancy must be followed up and reported to the sponsor's unique entry point on the Pregnancy Monitoring Form for Clinical Studies (Part B).

The ISF will contain the Pregnancy Monitoring Form for Clinical Studies (Part A and B).

As pregnancy itself is not to be reported as an AE, in the absence of an accompanying SAE and/or AESI, only the Pregnancy Monitoring Form for Clinical Studies and not the SAE form is to be completed. If there is an SAE and/or AESI associated with the pregnancy an SAE form must be completed in addition.

